1.1 TITLE AND TRIAL REGISTRATION

This SAP is the detailed statistical analysis plan, expanding the scientific IBBIS protocol of the two IBBIS randomized clinical trials (ClinicalTrials.gov Identifiers: NCT02872051 (RCT¹) and NCT02885519 (RCT²)):

RCT¹: “Integrated Mental Health Care and Vocational Rehabilitation to Individuals on Sick Leave Due to Anxiety and Depression (IBBIS)”

and

RCT²: “Integrated Mental Health Care and Vocational Rehabilitation to Individuals on Sick Leave Due to Stress Disorders (IBBIS)”.

Due to extensive methodological similarities between these studies this SAP applies to both, unless differences are mentioned explicitly.

1.2 SAP VERSION

This is the second version of the SAP.

¹ <https://clinicaltrials.gov/ct2/show/NCT02872051>

² <https://clinicaltrials.gov/ct2/show/NCT02885519>

Differences between version 1 and 2 are explicitly stated through a .docx-version of this newest version, where all changes are tracked, using the *Track changes* function in Microsoft Office Word. This file will be readily mailed through the corresponding author.

In brief, main changes revolves around the 24-month explorative outcomes: after analyses of 6- and 12-month outcomes we realized that results across work outcomes were heterogenous to a higher extent than expected. E.g., while the SAU group tended to have fastest RTW at 6-month follow-up, from explorative proportion over time-curves we realized that they might also tend to have a higher degree of recurrent sick-leave. Despite this, the SAU and INT groups still showed approx. the same number of weeks in work (when stability is disregarded) at 12-month follow-up. Followingly we speculate that the SAU group experiences faster RTW, but more recurrent sick leave. Therefore, we suggest that number of weeks in stable work is a better outcome, since this number is only high if RTW happens early, and if it is stable, and not disrupted by sick leave recurrence. We do though not know what stability threshold we should apply, and to *explore* this, we defined, prior to 24-month analyses, three different outcomes, with three different thresholds, see section 6.4. We plan these as sensitivity analyses.

1.3 PROTOCOL VERSION

Previous to publication of this SAP, plans have been described in both the protocol (published on clinicaltrials.org in the links provided), as well as in two study design articles (SDA), corresponding to the two RCTs^{2,3}.

2 INTRODUCTION: BACKGROUND, RATIONALE AND OBJECTIVES

Described thoroughly in the SDAs^{2,3}. Furthermore, the protocol was published³ on the official webpage of the organization (Mental Health Services, Capital Region of Denmark).

3 STUDY METHODS

3.1 TRIAL DESIGN

See SDAs^{2,3}.

3.2 RANDOMIZATION

From SDA²:

“The allocation ratio between the three arms is 1:1:1. A centralized randomization will take place according to a web-based computer-generated allocation sequence with varying block sizes kept unknown to the assessors. Odense Patient data Explorative Network (OPEN) is responsible for the randomization, administrative personnel in the IBBIS team perform the online randomization and the IBBIS team leader assign the participant to interventions and professionals.

We expect that service delivery can vary from municipality to municipality and the process of gaining a new job from unemployment will take longer time than returning to an existing job. Previous research has shown that diagnosis is a possible predictor of return to work⁴. Thus, the randomization is stratified according to 1) municipality 2) employment status (on sick leave from work vs. on sick leave from unemployment) 3) diagnosis [...]”

In RCT 1 diagnosis stratification is depression versus anxiety as primary diagnosis, and in RCT 2 diagnosis stratification is burnout vs. distress vs. adjustment disorder as primary diagnosis.

3.3 SAMPLE SIZE

Replicated from protocol follows:

³ <https://www.psykiatri-regionh.dk/Kvalitet-og-udvikling/udvikling/ibbis/Sider/IBBIS-forskning.aspx>

The sample size is based on a sample size calculation, using the 'Power and Sample Size' calculation programme⁴.

Type I error (α) risk

In each of the two RCTs we wish to conduct multiple comparisons (between 3 groups), and hence significance level must be as follows, due to Bonferroni correction:

$$\alpha = \frac{0,05}{3} = \frac{1}{60} = 0,0167$$

Type II error (β) risk

The organizational constellation of the interventions has not yet been trialled, and thus the desired power shall be set to:

$$\beta = 0,9$$

If it turns out that we cannot include enough participants, the power could be set to: $\beta = 0,8$

Hazard ratio (R)

The mean difference in time for return to work will be calculated as a hazard ratio. We estimate that as sufficient HR is

$$R = 1,5$$

since just 50 % faster return to work time in the intervention groups will convey a relevant economic benefit, due to the hence smaller loss of productivity.

Mean time to return to work (M_1)

Number of days from baseline to return to work is conservatively estimated to be 210 days, after an observed range from 104 to 210 days, in the control groups in three Dutch RCTs⁵⁻⁷, which were comparable to the control groups in the IBBIS RCTs.

Hence,

$$M_1 = 210$$

Inclusion time period (A)

We will include participants through 24 months,

$$A = 730[\text{days}]$$

Ratio between groups (m)

Ratio is 1:1:1, and hence $m = 1$

Follow-up time (F)

We will follow participants up for 365 days, in which they will contribute with risk time in the survival analysis, hence $F = 365$

Result

In each group, due to the above-mentioned variables, we need

198 participants per group, and with three groups that yields a need for, with power = 0.9,

⁴ <http://ps-power-and-sample-size-calculation.software.informer.com>

$$N = 198 \frac{\text{participants}}{\text{group}} \times 3 \frac{\text{groups}}{\text{trial}} = 594 \text{ participants}$$

If, in case of insufficient inclusion possibilities, power could be lowered to 0.8. In such case we would need the following number:

$$N = 153 \frac{\text{participants}}{\text{group}} \times 3 \frac{\text{groups}}{\text{trial}} = 459 \text{ participants}$$

3.4 STATISTICAL INTERIM ANALYSES AND STOPPING GUIDANCE

No interim analysis will be performed. We planned no stopping guidance.

3.5 TIMING OF FINAL ANALYSIS

The researchers who will perform the 6- and 12-month outcome analyses (AH and JF) will be blinded from intervention group allocation, until the primary outcome and all 12-month follow-up outcome main analyses are completed. The true randomization group allocation is concealed, with values X, Y and Z reflecting group allocation in the blinded dataset. The randomization allocation variable conversion formula is until unblinding only known and hidden by an administrative co-worker, who will not perform or assist any analysis.

At the time of publication of SAP version 1, baseline distributional analyses, and unadjusted estimated marginal means-analyses of self-reported numerical secondary outcomes at 6-month follow-up (and only these) have been calculated *blinded*, but will not be published, since this was not complying with the SDAs, nor any SAP version.

All 24-month follow-up analyses will be conducted unblinded.

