6.8.1 TIME TO RETURN TO WORK-OUTCOMES (OUTCOMES #1, #3 AND #8)

This section describes primary outcome *Time from baseline to RTW* at 12-month follow-up (1), and the secondary outcomes *Time from baseline to RTW* at 6- (outcome 3) and 24-month follow-up (outcome 8). The 24-month follow-up outcome will be calculated no earlier than June 2020. The other two, readily after the publication of this SAP, but before unblinding of analysts.

6.8.1.1 CALCULATION OF THE OUTCOME: SPECIFIC MEASUREMENT AND UNITS (AND TRANSFORMATION, WHERE APPLICABLE)

Time from baseline to RTW is defined as the number of weeks from randomization date, to stable return to work. Stable return to work is defined as 4 weeks consecutively in work, i.e. with no sick leave benefit those 4 weeks in the Dream register, and a so-called “branch code” in at least some of this 4 week period (benefit codes are week-based, branch codes are month based, and hence a period of 4 weeks may represent only one month, or overlap a two month period; in the latter case, return to work will be attained if at least one of these registrations contains a branch code; a branch code means that the individual received salary from an employer in this period). Time of event is first day of the four weeks.

These events will define censoring: 1) moving out of the country, 2) death, 3) public retirement pension (Da.: “Folkepension”), and 4) voluntary early retirement scheme (Danish: “Efterløn”).

At randomization all participants are, according to inclusion criteria, on sick-leave from employment or vacancy. Some participants might be on sick-leave from an employment in a *flexjob*⁷, and hence receiving *flexjob benefit* during employment. This benefit is changed to *flexjob sick-leave benefit* similar to regular sick leave benefit for participants not granted flexjob benefit prior to randomization. In these cases (of participants granted flexjob benefit prior to randomization) RTW is defined as either not receiving flexjob sick-leave benefit for four consecutive weeks, along with a registered branch code as above mentioned (or alternatively not receiving flexjob benefit, but an ordinary salary indicated by a branch code during those four weeks).

⁷ “Flexjob” is one of the Danish benefit schemes; it is a subsidy granted those with a chronic reduced work capacity

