6.8.1.4 STATISTICAL METHOD ASSUMPTION CONTROL

Assumptions for the proportional hazards (~Cox-) regression model are proportional hazards; this will be controlled performing af Schoenfeld (SF) test for residuals and visual inspection.

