6.8.3.5 ALTERNATIVE ANALYSIS METHOD IN CASE OF ASSUMPTION FAIL

In case of positive tests or visual inspections a robust variance estimator is used to correct standard errors.

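### The 24-month analyses lose the masking used earlier with nothing in its place, while two analysis choices remain open for exploratory outcomes

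*SAP*

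**What the plan says.** Section 3.5 of the SAP says that the analysts of the 6- and 12-month outcomes "will be blinded from intervention group allocation, until the primary outcome and all 12-month follow-up outcome main analyses are completed". The arms appear as X, Y and Z, and an administrative co-worker who does no analysis holds the key. The same section then states: "All 24-month follow-up analyses will be conducted unblinded". It gives no reason and no replacement measure.

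Section 1.2 explains why version 2 was written: "after analyses of 6- and 12-month outcomes we realized that results across work outcomes were heterogenous to a higher extent than expected". It names an arm ("while the SAU group tended to have fastest RTW at 6-month follow-up"), speculates that this arm also relapses more often, and proposes weeks in stable work as a better outcome. On the definition it says: "We do though not know what stability threshold we should apply". Three thresholds were therefore set before the 24-month analyses and labelled as sensitivity analyses.

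Two assumption checks involve looking at plots. For the time-to-return-to-work outcomes, 6.8.1.4 says of proportional hazards that "this will be controlled performing af Schoenfeld (SF) test for residuals and visual inspection". For the questionnaire outcomes, 6.8.3.5 says: "In case of positive tests or visual inspections a robust variance estimator is used to correct standard errors".

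**The concern.** The SAP treats masking as worth having up to 12 months. At 24 months the case for it is at least as strong, because section 1.2 records an arm-specific expectation that anyone working from version 2 has read. Where the plan leaves a choice between two defensible analyses, someone who sees the arms and expects a pattern can, without intending to, prefer the version that fits.

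At stake is the credibility of the 24-month findings, above all the weeks-in-work results, which are meant to explore the authors' own explanation of the earlier data. How much this matters depends on how many choices are really open and on what such a choice does to the error rate.

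**Working it through.** **Step 1. Which 24-month choices are open?**

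| Outcome | What the SAP fixes | What stays open |
|---|---|---|
| #8, time to return to work (secondary) | Event definition, Cox model and covariates as for the primary outcome (6.8.1.1–6.8.1.3). 6.8.1.5 acts on the Schoenfeld test at p < 0.05 and then follows a set order of models | The visual check in 6.8.1.4 triggers no action |
| Work and flexjob coding | Explicit rules on benefit weeks, branch codes, flexjob and vacancy (6.8.1.1, 6.8.4.1) | No judgement step found |
| #10–13, weeks in work | Thresholds of 4, 8 and 12 weeks set beforehand (1.2); test-driven sequence of count models (6.8.4.5) | Which analysis is the reference |
| 12 questionnaire outcomes (#18, 20, 22, 24, 26, 29, 32, 35, 38, 41, 44, 48; all exploratory) | Mixed model and covariates (6.8.3.2–6.8.3.3) | Robust or model-based standard errors, on a visual impression with no criterion (6.8.3.4–6.8.3.5) |
| #15 and harms | Descriptive only (6.8.5.2, 6.8.6.2) | No test |

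**Step 2. The weeks-in-work reference.** Section 6.2.2 makes #13, with stability disregarded, the pre-planned analysis and calls #9–12 sensitivity analyses of it. The first paragraph of 6.8.4.1 agrees, since it counts every qualifying week. The last paragraph of 6.8.4.1 instead says that the first analysis uses the stability definition of the primary outcome, at least 4 weeks, and then lists 4 weeks again among the sensitivity variants. The two cannot both be the reference.

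**Step 3. What could an arm-aware choice do to the error rate?** The level per contrast is 0.05/3 = 0.0167 two-sided (4.1), so each tail is p = 0.0167/2 = 0.0083 and the critical value is c = 2.394. Suppose there are two candidate analyses with null statistics Z1 and Z2 and correlation rho, and that the one more favourable to a given arm is always reported. Let b = P(Z1 > c and Z2 > c). Then:

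- favoured tail: P(max > c) = 2p − b
- opposite tail: P(max < −c) = b
- two-sided total: (2p − b) + b = 2p = 0.0167, whatever rho is.

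The SAP gives no correlations, so 0.8 to 0.95 is an assumption. By bivariate normal calculation:

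| rho | b (opposite tail) | favoured tail, 0.0167 − b | two-sided |
|---|---|---|---|
| 0.80 | 0.0030 | 0.0136 | 0.0167 |
| 0.90 | 0.0044 | 0.0122 | 0.0167 |
| 0.95 | 0.0055 | 0.0111 | 0.0167 |

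So the favoured tail rises from 0.0083 to about 0.011–0.014, and the opposite tail falls by the same amount.

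**Step 4. The standard-error choice.** Model-based and robust standard errors share one point estimate, so their test statistics are almost identical. In a simplified three-arm simulation (assumed skewed data, equal variances, 100–150 per arm, 20,000 runs) they correlated at about 0.999. At rho = 0.999, b = 0.0079 and the favoured tail is 0.0167 − 0.0079, about 0.0087, against 0.0083 nominally. For the 12 questionnaire outcomes the effect of this choice is therefore very small under those assumptions.

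**The case against.** The strongest reply is that unblinding follows naturally once the 12-month analysis is complete, that the SAP discloses it, and that little is left to choose. Most of this stands. Outcome #8 is the only secondary outcome at 24 months; its rules are numeric and repeat those of the primary outcome. The stable-work variants are declared as sensitivity analyses, which under 6.2 do not replace main results.

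Three stronger readings are tempting, and the document does not support them.

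- *That the two-sided error is inflated across all 24-month tests.* There are 18 tested outcomes (#8, #10–14 and the 12 questionnaire outcomes), hence 18 × 3 = 54 contrasts, and a reader might attach an error rate of 0.022–0.027 to each. That figure comes from picking the more significant of two results in either direction, which an analyst who sees only X, Y and Z could do equally well. It does not measure the effect of knowing the arms, and most of the 54 contrasts carry no open choice of the kind at issue.
- *That the visual check, or the coding of work records, leaves #8 open to judgement.* The plot changes no model, and the coding is rule-based.
- *That the people who saw the 12-month results will run the 24-month analyses.* Section 3.5 names analysts only for 6 and 12 months. Continuity is an inference from the first-person account in 1.2, although version 2 shows the arm pattern to any reader.

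It can also be said that re-masking is futile once allocation is known. That is right for re-using the letters X, Y and Z, because the earlier pattern would identify the arms. It does not apply to code written on randomly permuted labels, which carry no treatment signal. What stands against the objection is that disclosing the unblinding does not control it, and that two choices do remain open.

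**Conclusion.** The point holds as a modest, inexpensive improvement. Section 3.5 removes masking for every 24-month analysis without a substitute, after results by named arm had already shaped the 24-month work outcomes. The choices exposed are the visual trigger in 6.8.3.5 and the conflicting reference for weeks in work. All the outcomes concerned are exploratory.

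The risk is of possible directional bias. The favoured-tail figure of 0.011–0.014 assumes correlations of 0.95 to 0.8 and an analyst who always picks in one direction, so it is a ceiling under those assumptions and not a forecast. For the weeks-in-work reference the true correlation is unknown; for the standard-error choice the effect is far smaller. The 12-month primary result is unaffected, and nothing here shows that bias has occurred.

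**What to change.** - **Section 3.5.** State that all derivation and analysis code for the 24-month outcomes is written and frozen on a file in which arm labels have been randomly permuted within strata, that the true allocation is merged once after the freeze, and that any later change to the code is reported as a deviation.
- **Section 6.8.3.5.** Drop the visual trigger and use robust standard errors for all questionnaire outcomes.
- **Section 6.8.4.1.** Before the freeze, name #13 (stability disregarded) as the reference weeks-in-work analysis, in line with 6.2.2, and list the 4-, 8- and 12-week versions as sensitivity analyses only.

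The cost is a little extra programming to prepare the permuted file, plus the duty to report later code changes. No sample-size or data-collection change follows.

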4 STATISTICAL PRINCIPLES

4.1 CONFIDENCE INTERVALS AND P-VALUES

For all outcomes, the three randomization groups are pairwise compared. Due to these multiple comparisons, we will calculate 98,3% confidence intervals, according to Bonferroni correction of desired α -level of 0,05 in testing of 3 hypotheses:

$$\alpha\text{-level: } 0,05 \times \frac{1}{3} \cong 0,0167 \Rightarrow \text{Confidence Interval: } 1 - 0,0167 \cong 98,33\%$$

4.2 ANALYSIS POPULATIONS

All analyses are performed as *intention-to-treat*, unless otherwise stated.

5 TRIAL POPULATION

5.1 WITHDRAWAL AND FOLLOW-UP

Due to legislative circumstances participants can withdraw consent, and followingly all person sensitive data on these subjects will be deleted, yet participant ID number (not CPR number, but generated for this research project) and randomization result will be stored. In sensitivity analyses these ID numbers will be included, as described in “handling of missing data”.

5.2 BASELINE PATIENT CHARACTERISTICS

The following will be reported per RCT, per randomization allocation group. For all mean values of numeric variables, standard deviations will be reported.

| |
|---|
| Total number included in RCT and number in each randomization group |
| Age (mean, year) |
| Gender (%) |

| |
|---|
| Bech Depr. Inventory (mean) |
| Bech Anxiety Inventory (mean) |
| Work and Social adjustment Scale (mean) |
| Perceived Stress Scale (mean) |
| Employment status (% , employed vs. unemployed) |
| Primary diagnosis (%) |
| Municipality (%) |
| Sick leave duration at randomization (mean, days) |
| Educational level (% , short, moderate, long) |

Distributional balances of these covariates (except educational level, since this is only added in SAP v. 2, after primary baseline analyses) will be calculated using one way-ANOVA for numerical data and X² for categorical data, and analyses with $p \leq 0,05$ will define *imbalanced baseline covariates*.

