6.1 COVARIATE ADJUSTMENT IN GENERAL

Analyses will be adjusted for the three stratification variables, and no other, complying with RCT analysis guidelines from European Medicines Agency⁵.

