6.2 SENSITIVITY ANALYSES IN GENERAL

As sensitivity analyses, all outcome analyses will be performed adjusted for any unbalanced baseline covariates, as defined in 5.2, *Baseline patient characteristics*.

Results of sensitivity analyses are only interpreted as supplements to the main analysis and will not substitute main results.

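### The adjusted sensitivity analysis picks its covariates by baseline significance tests, so chance rather than prognostic value decides what, if anything, is added

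*SAP*

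**What the plan says.** Section 5.2 lists the baseline characteristics to be reported by arm and has them compared using "one way-ANOVA for numerical data and X² for categorical data". Results at p ≤ 0.05 "will define *imbalanced baseline covariates", with no allowance for the number of tests. Educational level is reported but not tested ("except educational level, since this is only added in SAP v. 2, after primary baseline analyses"), so it can never be selected.

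Section 6.2 gives the list its use: as sensitivity analyses, "all outcome analyses will be performed adjusted for any unbalanced baseline covariates". Neither section names a prognostic criterion or a fixed covariate list.

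Two other statements limit the reach of the rule. Section 6.1 fixes the main models: "Analyses will be adjusted for the three stratification variables, and no other". Section 6.2 adds: "Results of sensitivity analyses are only interpreted as supplements to the main analysis and will not substitute main results".

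**The concern.** Allocation is centralised and computer-generated (section 3.2), so apart from the stratification factors any baseline difference between arms is a chance difference. A significance test of balance then tests a null hypothesis that is true by construction. A variable is flagged about 5% of the time whether it predicts return to work strongly or not at all.

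How far an imbalance can move a treatment estimate depends on two things: the size of the imbalance and the strength of the variable's relation to the outcome. The rule looks only at the first, through a p-value. A strong predictor with a moderate imbalance stays out, and an irrelevant variable that happens to cross 0.05 goes in.

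Municipality, employment status and diagnosis are also tested, although randomisation is stratified on them and every main model already contains them. Flagging one of them changes nothing.

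At stake is the value of this one check. If nothing is flagged, the adjusted analysis is the main analysis under another name, and identical results could be taken for evidence of robustness to baseline differences.

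**Working it through.** The SAP gives no figure for how many covariates the rule would select, so there is none to reproduce.

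**Inputs**
- Tested variables (5.2, without educational level): age, gender, BDI, BAI, WSAS, PSS, employment status, primary diagnosis, municipality, sick-leave duration. That is 10.
- Already in the model (3.2, 6.1): municipality, employment status, diagnosis. That is 3.
- Variables that could be newly added: 10 − 3 = 7.
- Flagging probability per test under randomisation: 0.05.
- Arm sizes (3.3): 198 at power 0.9, 153 at power 0.8.

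**Step 1: how often the rule adds something, with independent tests**
- None added in a given trial: 0.95^7 = 0.698.
- At least one: 1 − 0.698 = 0.302.
- Expected number added: 7 × 0.05 = 0.35.
- Two or more: 0.044 (binomial, 7 tests at 0.05).
- None added in either of the two trials: 0.95^14 = 0.488.

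**Step 2: correlated scales**

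The four symptom and function scales are probably correlated, but the SAP gives no correlations. Six ANOVA tests and one chi-square test were simulated in three arms of 153 or 198, with the four scales correlated at 0 to 0.7 (an assumed range). The chance that nothing is added was about 70% to 75% per trial. At the upper end, the chance for both trials is about 0.75² = 0.56.

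**Step 3: what the rule can leave out**

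Take a numeric covariate with equally spaced arm means and a standardised difference d between the extreme arms. The ANOVA statistic is F = n·d²/4, so the largest unflagged difference is d = √(4·F_crit/n).
- n = 198: F_crit ≈ 3.01, d ≈ 0.25.
- n = 153: F_crit ≈ 3.02, d ≈ 0.28.

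If the covariate correlates r with a continuous outcome, the extreme-pair comparison shifts by about d·r/√(2/n) in z units. The SAP gives no r, so a range is shown:

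| Assumed r | Shift in z, n = 198 | Shift in z, n = 153 |
|---|---|---|
| 0.1 | 0.25 | 0.25 |
| 0.3 | 0.74 | 0.74 |
| 0.5 | 1.23 | 1.23 |

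For a weak predictor the missed imbalance hardly matters. For a strong one it could matter, and the rule cannot tell the two apart.

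**The case against.** The strongest reply is that nothing confirmatory depends on this rule. The main models are fixed in 6.1, and 6.2 makes the sensitivity results supplementary. A reader might infer that the primary result is biased, or that the planned robustness checks fail as a whole. The SAP supports neither. The rule governs only the covariate-adjusted supplement. The analyses for missing questionnaire data (6.2.1), for withdrawals and work-stability definitions (6.2.2) and for missing register data (6.7.1) do not depend on it.

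A reader might also infer that the adjusted analysis is in fact empty. That is not supported either. By section 3.5, baseline distributional analyses had been run, blinded, when SAP version 1 was published, so which variables were flagged is already settled; the SAP does not report it. The 70% describes the rule before data and one trial at a time. Across both trials it is close to even whether at least one gains a covariate. Nor is it a fault in itself that the two trials might adjust for different variables, since they are separate trials in different diagnostic populations.

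It can also be said that the rule is mechanical and uses no outcome data, whereas a replacement would be chosen after the 6- and 12-month results were known (section 1.2). This stands, and it limits how the fix may be presented at those time points. It does not make the rule informative.

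**Conclusion.** The point holds as a weakness of a supplementary analysis and is worth correcting. Selection by baseline p-value reflects chance and ignores prognostic strength, and three of the ten tests cannot change any model. A priori, a given trial has about a 70% chance of an adjusted analysis identical to the main one (70% to 75% with correlated scales), and the chance is about 49% for both trials together (about 56% at the upper end of the assumed correlations). These figures rest on valid randomisation and on the stated independence or correlation assumptions. The shift of up to about 1.2 in z is illustrative, because the SAP gives no correlation between any covariate and an outcome. Main estimates, their confidence intervals and the other sensitivity analyses stand as planned.

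**What to change.** 1. In 5.2, drop the balance tests as a selection rule and present the baseline table descriptively.
2. In 6.2, name one fixed covariate set for all modelled outcomes in both trials: the stratification variables plus sick-leave duration at randomisation, age, gender, and baseline BDI, BAI, PSS and WSAS.
3. For questionnaire outcomes, leave out the outcome's own baseline score, because section 6.8.3.1 already uses it as an observation in the mixed model.
4. Exclude the outcomes that are only described and have no model to adjust: number 15 (6.8.5.2) and numbers 49 to 64 (6.8.6.2).
5. Apply the fixed set prospectively to the 24-month analyses. For the 6- and 12-month outcomes, report it as a dated and labelled later addition, next to the sensitivity analysis already planned.

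The variables are all in the 5.2 table, so no new data are needed. The cost is a change of SAP wording, one extra model per modelled outcome, and a post hoc label on the 6- and 12-month results.
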